6. SUBJECT WITHDRAWAL AND STUDY TERMINATION

6.1. Subject Withdrawal

6.1.1. Discontinuation of Study Drug

Subjects must be discontinued from study drug for:

- Pregnancy

In addition, subjects may be discontinued from study drug for any of the following reasons:

- AE
- Protocol deviation, including non-compliance with dosing regimen
- Lost to follow-up (defined as no contact after 3 documented attempts by phone followed by 1 attempt via certified letter)
- Subject request
- Investigator request
- Death

6.1.2. Withdrawal from Study

Subjects have the right to withdraw from the study at any time without prejudice. Study drug must be discontinued and no further assessments conducted. Further attempts to contact the subject are not allowed unless safety findings require communication or follow-up. Patients withdrawing after enrollment but prior to receipt of study drug will be considered screen failures.

Subjects may also be discontinued from the study for the following reasons:

- Subject request
- Investigator request
- Lost to follow-up (defined as no contact after 3 documented attempts by phone followed by 1 attempt via certified letter)
- Discontinuation of the study by the IND Office, or the supporting drug company
- Study complete
- Death

6.2. Study Termination

End of Trial is defined as the time at which all patients enrolled in the study have completed the last study visit and data from those visits have been reviewed by the Investigator or designee.

Premature termination of this study may occur at any time because of a regulatory authority decision, change in opinion of the IRB, drug safety concerns, or at the discretion of the IND Office, or the supporting drug company. In addition, the IND Office, or the supporting drug company retains the right to discontinue development of infigratinib at any time. If termination becomes necessary, the IND Office, or the supporting drug company will inform the appropriate regulatory authorities of the termination and the reason. The Principal Investigator will inform the IRB of the same. In terminating the study, the IND Office, or the supporting drug company and the Principal Investigator will assure that adequate consideration is given to the protection of the patients' interests.

7. STUDY VISITS AND PROCEDURES

7.1. Main Informed Consent

The subject will sign the study's informed consent form (ICF) prior to conducting any study-specific procedures. The study team will be allowed to use standard of care assessments/procedures that were done prior to obtaining consent if these fall within the allowed time window.

7.2. Screening (Day -28 to -1)

After the main ICF is signed, screening activities will include the following:

- Collection of blood, tissue and urine for correlative studies
- Demography
- ECOG performance status
- Relevant medical history/current medical conditions
- Diagnosis and extent of cancer
- Prior anticancer therapy
- Height and weight
- AEs
- Prior medication use
- Physical examination
- Vital signs
- Ophthalmic assessment
- Blood draw for hematology, chemistry, and coagulation assessment
- Urinalysis (macro, micro only if necessary)
- Pregnancy test (blood or urine) for WOCBP (within 7 days before first dose of study drug)
- 12-lead ECG
- Cardiac imaging(ECHO)
- URS/Tumor Mapping
- EORTC QLQ-C30 QOL Questionnaire

7.3. Treatment Period: Day 1

Before the start of dosing on Day 1, the following assessments are to be performed. Baseline/screening assessments that are conducted within 7 days prior to first treatment can be used to satisfy the Day 1 requirement.

- Weight
- Prior and concomitant medication use
- Symptom-directed physical examination (if needed)
- Vital signs
- Blood draw for hematology, chemistry; blood draw for coagulation, if clinically indicated
- Urinalysis (micro- or macroscopic), if clinically indicated
- Pregnancy test (blood or urine) for WOCBP
- AEs

7.4. Rest of Treatment Period

Throughout the treatment period, subjects will be monitored for AEs and concomitant medication use. Other safety assessments, including symptom-directed physical examinations; vital signs; ophthalmic assessment, laboratory measures (hematology, blood chemistry, coagulation, pregnancy) and urinalysis; and 12-lead ECG and cardiac imaging will be conducted at the times indicated in the schedule of assessments in Section 1. (Note: Blood draws for laboratory measures may be drawn and measured at a local diagnostic lab)

7.5. Pre-op Visit

All patients will be required to return to clinic for pre-operative assessment within 14 days prior to the surgical procedure. Assessments will include the following:

- Weight
- Concomitant medication use
- Physical examination
- Vital signs
- Blood draw for hematology, chemistry
- Collection of blood and urine for correlative studies
- Pregnancy test (blood or urine) for WOCBP
- 12-lead ECG
- AEs
- EORTC QLQ-C30 QOL Questionnaire

NOTE: Collection of tissue for correlative studies **at surgery**

7.6. 30-day Safety Follow-up Visit

All subjects must complete safety follow-up assessments 30 days (+/- 14 days) after the last dose of the study drug or surgery, whichever occurs last. Information relating to anticancer therapies taken since discontinuation of study drug and AEs (including concomitant medication taken for ongoing AEs) will be collected for 30 days after the last dose of the study drug. Assessments will include the following:

- Vital signs
- Ophthalmic assessment (per treating physician's discretion)
- Blood draw for hematology, chemistry
- Urinalysis (macro, micro only if necessary)
- Collection of blood and urine for correlative studies
- Pregnancy test (blood or urine) for WOCBP
- EORTC QLQ-C30 QOL Questionnaire

7.7. End of Study

All subjects must complete one last visit approximately one year (+/- 30 days) after discontinuation or study treatment or surgery, whichever occurred last. Assessments will include the following:

- Relevant medical history/current medical conditions
- Physical examination
- Vital signs
- Blood draw for hematology, chemistry
- CT scan and cystoscopy(+/- URS)

8. STUDY ASSESSMENTS

8.1. Efficacy Assessments

Efficacy will be assessed by tumor response to study drug. To assess each subject's response, the surgical specimen will be assessed/compared against the pre-treatment tumor mapping (Section 12.3, Appendix 3)

Table 3: Response Criteria for UTUC Lesions

Response criteria	Evaluation of target lesions
Complete Response (CR):	Disappearance of all target lesions as documented in Tumor Mapping.
Partial Response (PR):	At least a 30% decrease in the sum of diameter of all mapped lesions, taking as reference the baseline sum of diameters.
Progressive Disease (PD):	At least a 20% increase in the sum of diameters of mapped lesions, taking as reference the smallest sum on study (this includes the baseline sum if that is the smallest on study). In addition to the relative increase of 20%, the sum must also demonstrate an absolute increase of at least 5 mm. ^a Or the appearance of one or more new lesions.
Stable Disease (SD):	Neither sufficient shrinkage to qualify for PR nor sufficient increase to qualify for PD, taking as reference the smallest sum diameters while on study.

Abbreviations: CR, complete response; PD, progressive disease; PR, partial response; SD, stable disease.

^a The appearance of one or more new lesions is also considered progression.

Source: [Eisenhauer et al 2009](#)

Table 4 (NOT APPLICABLE TO THIS STUDY, KEPT FOR TABLE REFERENCING): Response Criteria for Non-target Lesions

Response criteria	Evaluation of non-target lesions
Complete Response (CR):	Disappearance of all non-target lesions and normalization of tumor marker level.
Progressive Disease (PD):	Unequivocal progression of existing non-target lesions or the appearance of one or more new lesions.
Non-CR/Non-PD:	Persistence of one or more non-target lesion(s) and/or maintenance of tumor marker level above the normal limits.

Abbreviations: CR, complete response; PD, progressive disease.

Source: [Eisenhauer et al 2009](#)

Note: Unequivocal progression in non-target lesions must be substantial and generally sufficient to require change in

therapy. The increase in overall disease burden should be comparable in magnitude to the increase that would be required to declare PD for measurable disease: i.e. an increase in tumor burden representing an additional 73% increase in 'volume' (which is equivalent to a 20% increase diameter in a measurable lesion).

Table 5: Overall Lesion Response at each Assessment

Target lesions	Non-target lesions	New lesions	Overall lesion response
CR	CR	No	CR
CR	Non-CR/Non-PD	No	PR
CR	Not evaluated	No	PR
PR	Non-PD or not all evaluated	No	PR
SD	Non-PD or not all evaluated	No	SD
Not all evaluated	Non-PD	No	NE
PD	Any	Yes or No	PD
Any	PD	Yes or No	PD
Any	Any	Yes	PD

Abbreviations: CR, complete response; NE, not evaluable; PD, progressive disease; PR, partial response; SD, stable disease.

Source: [Eisenhauer et al 2009](#)

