2.7. Endpoints

The primary endpoint is the proportion of patients who are not able to complete treatment due to excessive toxicity. Toxicity will be tabulated by type, frequency, and severity of AEs and serious AEs (SAEs), laboratory abnormalities, and other safety findings.

The secondary endpoints are:

- Percentage of patients achieving a point in time objective response (either complete or partial response [CR or PR]) after 2 cycles of infigratinib. Tumor mapping will be performed from the endoscopic evaluation (after any biopsies) and this will be used to compare to pathologic (NUX/Ux cohort) or ureteroscopic (endoscopy cohort) findings in order to determine responses.
- Tumor mapping will be performed based on endoscopic findings, noting location, number of tumors, tumor architecture, and location of biopsies; and will again be performed during pathologic evaluation again noting size, location, number of tumors, architecture, and absence of tumor at any previously identified tumor. A difference of 3mm will be considered within error of measurement.
- Mutational analysis will be performed on FFPE tumor tissue using a comprehensive mutation panel (T200.2) which we have used in prior studies and includes all previously identified UTUC mutations, including all relevant FGFR3 alterations including hot spots, copy number variations and fusions. Blood collected at baseline will be used as germline source.
- All analyses will be performed on patients stratified as having or not having FGFR3 alterations. Descriptive statistics will be used to summarize various clinical parameters.
- The same methods will also be used to explore the association of AEs such as hyperphosphatemia with response.
- Percentage of patients with no evidence of disease 12 months after surgery

- Changes in patient reported QOL outcomes will be measured using a validated questionnaire (EORTC QLQ-C30 v3), administered at 3 time points: 1. enrollment (after enrollment and before first dose), 2. after completion of 2 cycles and prior to surgery, and 3. at 1 month postoperative check.

The exploratory endpoints are:

Tumor Studies:

- Single cell (sc)RNAseq will be performed on fresh frozen tumors using 10x Genomics platform. Tumor cell heterogeneity, FGFR3 gene expression, and tumor microenvironment will be profiled. All bioinformatics data analysis will be performed in the MD Anderson Genomics core as part of the Rare Tumor Initiative Program (2014-0938)

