8.2.7. Ophthalmic Assessments

Ophthalmologic examination will be performed by an ophthalmologist, or optometrist who is supervised by an ophthalmologist, at the times indicated in [Section 1](#). These assessments will include visual acuity testing, slit lamp examination of the anterior eye segment, intraocular pressure, and fundoscopy. Additional examinations such as specular microscopy (that enables a magnified, direct view of the corneal epithelium), corneal pachymetry, retinal optical coherence tomography (OCT), and dilated fundoscopy will be performed as clinically indicated.

9. STATISTICAL PLAN:

The primary objective is to evaluate the safety and tolerability of infigratinib as neoadjuvant therapy. Up to 20 patients will be enrolled in the study. The study will estimate proportion of patients who are not able to complete treatment (discontinuation) due to excessive toxicity along with the 90% exact confidence interval (NOTE: excessive toxicity is defined as treatment related adverse events that cause patients not to complete 2-cycles of planned treatment schedule). Toxicities will be tabulated using frequency and percentage by grade and their relations to treatment. Assuming a 30% of discontinuation due to excessive toxicity, the 90% confidence interval would be (13.1%, 46.9%) with a sample size of 20. Toxicity data will be summarized for the whole group of patients and for patients with eGFR \geq 50 and eGFR 30-49 separately. The safety analysis included all patients who received at least one dose of infigratinib.

Toxicity monitoring:

The study will monitor the incidence of not completing treatment or delay >14 days of surgery due to excessive toxicity using this monitoring rule. That is stop the trial early if $\text{Prob}(\text{Ptox} > 0.3 | \text{data}) > 0.85$. Where Ptox denotes the proportion of patients not being able to complete treatment or delay >14 days of surgery. The corresponding stopping boundaries are that the trial will be stopped early if at any time it is observed that $(n \text{ of patients not completing treatment or delay } >14 \text{ days of surgery due to excessive toxicity} / N \text{ of patients treated}) \geq 3/5, 4/(6-8), 5/(9-10), 6/(11-13), 7/(14-16), \text{ and } 8/(17-19)$. This stopping rule will be applied for each cohort of eGFR \geq 50 and eGFR 30-49 separately. If one cohort stops early due to excessive toxicity, the other will continue accruing as per protocol criteria and toxicity monitoring rule.

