The following table displays the operating characteristics for safety monitoring, assuming prior distribution for Ptox is beta(0.3, 0.7) and for a maximum sample size of 20. Since we do not have information for proportions of eGFR \geq 50 and eGFR 30-49, it would not be feasible to assess OCs for each cohort.

OCs for toxicity monitoring using a maximum sample size of 20

Rate of discontinued treatment due to toxicity/intolerance	Probability of early stop	Avg. N of patients treated
0.1	0.012	19.8
0.2	0.10	18.7
0.3	0.341	16.0
0.4	0.655	12.4
0.5	0.886	9.0

The secondary efficacy endpoint is objective response after 2 cycle treatment of infigratinib. We will estimate the objective response rate along with the 90% confidence interval. Fisher's exact test will be used to explore the difference in response between the two cohorts of patients.

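### Partial response has no absolute minimum decrease, so at baseline sums of 10 mm or less a change the plan treats as measurement error can be scored as a response

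*Combined protocol and SAP*

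**What the plan says.** - **PR rule (Section 8.1, Table 3):** "At least a 30% decrease in the sum of diameter of all mapped lesions, taking as reference the baseline sum of diameters". The row gives no absolute minimum.
- **Progression rule (same table):** "In addition to the relative increase of 20%, the sum must also demonstrate an absolute increase of at least 5 mm". This row does carry a minimum in millimetres.
- **CR rule (same table):** "Disappearance of all target lesions as documented in Tumor Mapping". No minimum baseline lesion size is attached.
- **Measurement error (Section 2.7, repeated in Appendix 4):** "A difference of 3mm will be considered within error of measurement". The sentence closes the description of tumor mapping.
- **Use of the maps (Section 2.7):** the endoscopic baseline map is the reference, and "this will be used to compare to pathologic (NUX/Ux cohort) or ureteroscopic (endoscopy cohort) findings in order to determine responses".
- **Endpoint (Section 9):** "The secondary efficacy endpoint is objective response after 2 cycle treatment of infigratinib". The response rate is to be reported with a 90% confidence interval. On sample size: "Up to 20 patients will be enrolled in the study".

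Table 3 and Section 9 do not mention the 3 mm sentence. The documents do not say whether 3 mm applies to each lesion or to the sum, or which rule governs when they disagree. No minimum lesion size appears in Sections 4.1 and 4.2, in Table 3, or on the mapping forms in Appendix 3.

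**The concern.** Two rules act on the same measurements and can disagree. An 8 mm lesion later measured at 5 mm has shrunk by 37.5%. That is a PR under Table 3 and no detectable change under Section 2.7. Two assessors who both follow the protocol could score this patient differently.

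Small baseline sums are plausible. Section 4.1 admits low-grade disease and ureteroscopic management, and the background in Section 2 links endoscopic treatment to low-volume disease. In the nephroureterectomy/ureterectomy cohort the baseline is endoscopic and the follow-up pathologic, so two different methods are being compared.

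What is at stake is the secondary objective response rate and the analyses that use response: FGFR3 alteration, cfDNA, expression markers, urinary mutations and adverse events. With at most 20 patients, one misclassified patient moves the response rate by at least 1/20 = 5 percentage points.

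**Working it through.** The plan gives no error rate for its response rule, so there is no figure to reproduce.

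**Inputs from the documents:** PR threshold 30% of the baseline sum (Table 3); stated error 3 mm (Section 2.7, Appendix 4).

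**Step 1: where the rules overlap.** A decrease of 3 mm from a baseline sum S meets the PR rule when 3/S ≥ 0.30, that is S ≤ 3/0.30 = 10 mm.

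| Baseline sum (mm) | 3 mm as % of sum | PR under Table 3? |
|---|---|---|
| 5 | 60.0 | yes |
| 6 | 50.0 | yes |
| 8 | 37.5 | yes |
| 10 | 30.0 | yes (the rule says at least 30%) |
| 11 | 27.3 | no |
| 15 | 20.0 | no |

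If 3 mm is a per-lesion error and all k lesions err in the same direction, the condition is 3k/S ≥ 0.30, or S ≤ 10k. That is 20 mm for two lesions and 30 mm for three, a mean lesion size of 10 mm or less.

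**Step 2: illustrative chance of a false PR.** Assume one patient with no true change and a normal, unbiased difference between the two measurements of the sum, with standard deviation SD. As written, the chance is Φ(−0.30·S/SD). With an added requirement of more than 3 mm it is Φ(−max(3, 0.30·S)/SD). The documents do not say what 3 mm represents, so SD is an assumption, shown over a range: a 95% limit (3/1.96 = 1.53 mm), a 90% limit (3/1.645 = 1.82 mm), or one SD (3.0 mm).

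Example, S = 5 and SD = 1.53: Φ(−1.5/1.53) = 16.4% as written, and Φ(−3/1.53) = 2.5% with the minimum.

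| Meaning of 3 mm (assumed) | 5 mm: as written → with minimum | 8 mm: as written → with minimum |
|---|---|---|
| 95% limit | 16.4% → 2.5% | 5.8% → 2.5% |
| 90% limit | 20.5% → 5.0% | 9.4% → 5.0% |
| One SD | 30.9% → 15.9% | 21.2% → 15.9% |

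Above 10 mm the added minimum changes nothing, because 30% of the sum already exceeds 3 mm.

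**Step 3: what a minimum on the sum leaves open.** Three 8 mm lesions, each measured 2.5 mm smaller, give 7.5/24 = 31.25%. That is a PR even with a minimum of more than 3 mm on the sum, although every lesion is within the stated error. Likewise, a sole lesion of 3 mm or less that is not found again changes by no more than the stated error, yet it counts as a CR.

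**The case against.** The strongest reply is that the 3 mm sentence is already the floor. It belongs to the mapping description, the maps are what Table 3 is applied to, and so differences up to 3 mm would be set to no change before scoring. That reading is possible. But Table 3 does not state it, no cross-reference supports it, and it leaves open whether lesions or the sum are meant. Applied literally, Table 3 scores within-error changes as responses. If the implied floor is what was intended, the same amendment is needed to say so.

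It is also fair to object that a floor has a price. Requiring more than 3 mm raises the effective PR threshold to over 60% at a 5 mm sum and over 37.5% at 8 mm, so some true responses are lost. This stands, and it is part of the cost of the fix.

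Three stronger readings are tempting, and the documents do not support them:

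- **That the progression minimum ("the sum must also demonstrate an absolute increase of at least 5 mm") biases the response rate upward because PR has none.** Response is CR or PR. The progression minimum only moves patients between progressive and stable disease, and both are non-response. The contrast shows only that Table 3 can carry an absolute minimum.
- **That this undermines the study's main result or the basis for a later phase 2 trial.** The primary endpoint is treatment discontinuation for toxicity. Sections 2 and 2.5.1 tie the future study to tolerability and biologic consequences, and Section 9 expects the analyses to be probably only descriptive at this sample size.
- **That the percentages above measure bias in this trial.** They apply to one unchanged patient with a given small sum. No distribution of lesion sizes is given.

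**Conclusion.** The point holds as an unreconciled conflict between two rules. At a baseline sum of 10 mm or less (or a mean lesion size of 10 mm or less, if the error is per lesion and runs in one direction), the same 3 mm decrease is both a PR and within the plan's stated error. Measurement error alone can then be counted as response. The overlap is arithmetic and needs no assumption beyond the plan's own figures.

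The size is less certain. The false-PR chances, from about 6% to 31% across 5 and 8 mm sums, rest on assumed SDs and an unbiased normal error. The net effect on the reported response rate cannot be derived from the documents. The consequence is confined to the secondary response endpoint and the analyses built on it; the primary tolerability endpoint and the toxicity stopping rule are untouched. The correction is worth making because it is short and uses the plan's own 3 mm figure.

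**What to change.** Before any response is scored:

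1. Amend the PR row of Table 3 to require at least a 30% decrease in the sum of diameters **and** an absolute decrease of more than 3 mm in the sum, with a cross-reference to Section 2.7 and Appendix 4.
2. State whether the 3 mm error applies to each lesion or to the sum. If per lesion, state that a lesion difference of 3 mm or less is counted as no change when the sum is formed.
3. State how a baseline lesion of 3 mm or less that is not found again counts toward CR.

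The cost is a few sentences in the protocol. The reported response rate may be slightly lower, and some true small shrinkages will be scored as stable disease: a real change from 5 to 3 mm (40%) would no longer be a PR. False responses are not removed altogether; if 3 mm is one SD, the chance with the minimum is still about 16% at sums of 10 mm or less.

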8.2. Safety Assessments

The investigator (or physician designee) is responsible for verifying and providing source documentation for all adverse events and assigning the attribution for all adverse events for subjects enrolled.

The safety evaluation will be based on AE reporting, laboratory parameters, vital signs, physical examinations, 12-lead ECGs, cardiac imaging, and ophthalmic assessments. Tolerability will be assessed by the incidence of AEs leading to study drug discontinuation.

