Adverse events leading to study drug discontinuation were reported in a total of 14.4%. Most commonly reported AEs leading to discontinuation of study drug, in all patients, by preferred term were: visual impairment, hypercalcemia, hypercreatininaemia, hyperlipesaemia, and palmar-plantar erythrodysaesthesia syndrome in 1.0% each. Twenty-one patients (10.1%) discontinued treatment due to AEs that were suspected to be related to study treatment. The common suspected AEs leading to study treatment discontinuation were: visual impairment, hypercalcemia, hypercreatininaemia, hyperlipasaemia, and palmar-plantar erythrodysaesthesia syndrome in 1.0% each.

AEs requiring dose interruption or reduction occurred in 68.3% of patients. The most common AEs (incidence $\geq 10\%$) requiring dose adjustment or temporary interruptions regardless of study drug relationship were hyperphosphatemia (28.8%) and hypercreatininaemia (15.9%).

Overall, Grade 3 hematology abnormalities were reported in 13.9%, of which, two SAEs of anemia were reported in 2 patients (one patient had Grade 2 anemia and the other had Grade 3 anemia). New or worsened Grade 4 hematology abnormality of lymphocytes decrease was reported in 1.5% of patients.

Eye-related AEs were reported in a total of 44.7% of patients. Of these, AEs suspected to be study treatment related were reported in 33.7%. There was one Grade 2 SAE of keratitis reported which was suspected to be treatment related and led to study drug discontinuation ([BGJ398X2101 Clinical Study Report; Pal et al 2018](#)).

Please refer to the Infigratinib Investigator Brochure for additional safety information.

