2.6. Objectives

The **primary objective** is to evaluate the tolerability of infigratinib in patients with low-grade and high-grade platinum ineligible UTUC.

The **secondary objectives** are to:

- Assess tolerability in those with GFR 30-49
- Evaluate the objective response rate (CR+PR) of infigratinib after 2 cycles in UTUC with and without FGFR3 alterations
- Correlate tumor tissue FGFR3 alteration (presence/absence, alteration type, and clonal status) with response and occurrence/severity of AEs such as hyperphosphatemia

- Evaluate, bladder and local/distant recurrence within 12 months in those undergoing NUX/Ux and upper tract, bladder, and local/distant recurrence within 12 months in those undergoing endoscopic management.
- Evaluate renal function pre-treatment and after two treatments.
- Evaluate patient-reported quality of life (QOL) outcomes during treatment.

The **exploratory objectives** are to:

- Explore intra-tumor heterogeneity, gene expression profiles, and changes in tumor microenvironment using single cell RNA sequencing (scRNA-seq) and CyTOF pre and post treatment to identify potential mechanisms of response and/or resistance, and correlation with the occurrence/severity of AEs.
- Explore urinary/upper tract washing FGFR3 alterations as potential biomarker for detection and response
- Explore cfDNA for detection of FGFR3 alterations and as a predictor of response

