8.2.1. Adverse Events

8.2.1.1. Definitions

An Adverse Event is defined as any untoward medical occurrence in a patient regardless of its causal relationship to study treatment. An AE can be any unfavorable and unintended sign (including any clinically significant abnormal laboratory test result), symptom, or disease temporally associated with the use of the study treatment, whether or not it is considered to be study drug(s) related. Included in this definition are any newly occurring events and any previous condition that has increased in severity or frequency since the administration of study therapy. An SAE is defined as one of the following:

- Is fatal or life-threatening
- Results in persistent or significant disability/incapacity
- Constitutes a congenital anomaly/birth defect
- Is medically significant, i.e., defined as an event that jeopardizes the subject or may require medical or surgical intervention to prevent one of the outcomes listed above
- Requires inpatient hospitalization or prolongation of existing hospitalization, unless hospitalization is for:
 - Routine treatment or monitoring of the studied indication, not associated with any deterioration in condition
 - Elective or pre-planned treatment for a pre-existing condition that is unrelated to the indication under study and has not worsened since signing the informed consent
 - Treatment on an emergency outpatient basis for an event not fulfilling any of the definitions of a SAE given above and not resulting in hospital admission
 - Social reasons and respite care in the absence of any deterioration in the subject's general condition

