8.2.1.3. Recording Adverse Events

AEs will only be captured if they are \geq Grade 3 and are reported to be causally related with the investigational study drug.

Conditions already present at the time of informed consent should be recorded in the Medical History eCRF. These baseline conditions will be graded at study entry and monitored throughout the study. If at any point there is a worsening of the baseline condition to \geq Grade 3 this will also be captured in the eCRF and reported accordingly.

AEs (including lab abnormalities that constitute AEs) should be described using a diagnosis whenever possible, rather than individual underlying signs and symptoms. When a clear diagnosis cannot be identified, each sign or symptom should be reported as a separate AE.

AEs exclusively related to surgery will not be collected in the database.

The following information is to be captured in the eCRF for each AE: severity grade (CTCAE v5.0 Grade 1-5); duration (start and end dates); relationship to study drug (reasonable possibility that AE is related: No, Yes); action taken with respect to study drug (none, dose reduction, temporarily interrupted, permanently discontinued, unknown, not applicable); whether medication or therapy was given (no concomitant medication/non-drug therapy given, concomitant medication/non-drug therapy given); outcome (not recovered/not resolved, recovered/resolved, recovering/resolving, recovered/resolved with sequelae, fatal, unknown); and whether the event is serious and seriousness criteria.

AE monitoring should be done from the time of informed consent and continue through 30 days after the last dose of study drug.

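### The adverse event capture rule in Section 8.2.1.3 is too narrow for the discontinuation measures planned in Sections 8.2, 9 and 9.1.1.1

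*Combined protocol and SAP*

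**What the plan says.** The primary objective (Section 2.6) "is to evaluate the tolerability of infigratinib in patients with low-grade and high-grade platinum ineligible UTUC". Section 2.7 sets the endpoint: "The primary endpoint is the proportion of patients who are not able to complete treatment due to excessive toxicity". It does not define excessive toxicity. Section 9 does, in a note beside the estimator: "excessive toxicity is defined as treatment related adverse events that cause patients not to complete 2-cycles of planned treatment schedule". That definition requires relatedness and sets no grade threshold. The toxicity stopping rule in Section 9 uses the same term and adds surgery delayed by more than 14 days.

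Section 8.2 describes the measure more loosely: "Tolerability will be assessed by the incidence of AEs leading to study drug discontinuation". It carries no relatedness qualifier, and Section 8.2.1.1 defines an AE as "any untoward medical occurrence in a patient regardless of its causal relationship to study treatment".

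Section 9.1.1.1 plans incidence tables for all treatment-emergent, serious, treatment-related and serious treatment-related AEs, with separate tables for AEs leading to discontinuation. It also plans listings or narratives of discontinuations due to AEs.

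Section 8.2.1.3 restricts what is recorded: AEs are captured only if they are Grade 3 or higher and "are reported to be causally related with the investigational study drug". The stated exception is a baseline condition that worsens to Grade 3 or higher.

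**The concern.** The analysis sections ask for data that the recording section tells sites not to collect. Two groups of patients who stop treatment are affected.

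The first stop for a related AE below Grade 3. They meet the Section 9 primary definition, yet the AE would not be captured. The second stop for an AE judged unrelated. They fall outside the Section 9 definition but inside the Section 8.2 sentence and the Section 9.1.1.1 discontinuation table.

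The first group bears on the primary estimate and the stopping count. The second bears on whether anyone can check the attribution behind them. This is a single-arm trial and Section 8.2 makes the investigator responsible for attribution, so no control rate exists to set against that judgement. An AE that was never recorded may also be hard to reconstruct at analysis.

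**Working it through.** **1. The plan's own figure.** Section 9 assumes 30% discontinuation in 20 patients and gives a 90% interval of 13.1% to 46.9%. The normal approximation reproduces it: 0.30 ± 1.645 × √(0.30 × 0.70 / 20) = 0.30 ± 0.169. The exact 90% interval for 6/20 is 14.0% to 50.8%. Section 9 names an exact interval, so the printed one does not match its label. That is a separate matter; exact intervals are used below.

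**2. Which treatment-ending AEs are captured.**

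| AE that ends treatment | Captured? | Section 9 primary event? | Within Section 8.2 as worded? |
|---|---|---|---|
| Related, Grade 3 or higher | Yes (8.2.1.3) | Yes | Yes |
| Serious, any grade or attribution | Yes (8.2.1.4) | If related | Yes |
| Laboratory, requiring dose modification or interruption | Yes (8.2.3) | If related | Yes |
| Baseline condition worsening to Grade 3 or higher | Yes (8.2.1.3) | If related | Yes |
| Related, below Grade 3, non-serious, non-laboratory | **No** | **Yes** | **Yes** |
| Unrelated, non-serious, non-laboratory, not a worsened baseline condition | **No** | No | **Yes** |

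**3. The fifth row is not hypothetical.** Table 2, which covers AEs considered possibly related, provides for discontinuation with Grade 2 pancreatitis, Grade 2 neurotoxicity or uncontrolled Grade 2 vomiting not resolved within 14 days, Grade 2 central serous retinopathy resolving after more than 14 days, and retinal vein occlusion from Grade 1. Unresolved Grade 2 creatinine elevation and hypercalcemia are also listed, but Section 8.2.3 recovers those. These rules are cited only to show that such events can arise; no view is taken on them.

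**4. Size for the primary estimate.** One patient in 20 is 1/20 = 5 points. The number missed is an assumption, shown from the plan's own 30%:

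| Events counted | Estimate | Exact 90% CI |
|---|---|---|
| 6/20 (none missed) | 30% | 14.0% to 50.8% |
| 5/20 (one missed) | 25% | 10.4% to 45.6% |
| 4/20 (two missed) | 20% | 7.1% to 40.1% |

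**5. Size for the stopping rule.** The first boundary is 3 of 5, applied to each eGFR cohort separately. If one of three qualifying events is not captured, the count reads 2 of 5 and the cohort continues. The same one-event shortfall applies at every later boundary.

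**6. Size for attribution.** Section 2.4.2 reports discontinuation for any AE in 14.4% and for suspected related AEs in 21 patients (10.1%). The implied denominator is 21/0.101 ≈ 208; Section 2.4.2 also gives 57 deaths as 27.4%, and 57/0.274 ≈ 208. On 208 patients, 14.4% is 30.

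- Difference: 14.4 − 10.1 = 4.3 points; ratio 14.4/10.1 = 1.43.
- In 20 patients: 20 × 0.144 = 2.88 against 20 × 0.101 = 2.02, a gap of 0.86 patient.
- Exact 90% CIs at the nearest counts: 3/20, 4.2% to 34.4%; 2/20, 1.8% to 28.3%.

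**The case against.** A reader might infer that the primary outcome has two competing definitions, about 4 points apart. The documents do not support that. Section 2.7 names the primary endpoint and Section 9 defines its key term next to the estimator and the stopping rule. The Section 8.2 sentence does not mention a primary endpoint and plays no part in either calculation. Its any-cause reading is an inference from the missing qualifier and the AE definition in Section 8.2.1.1. The looseness in Section 8.2 is a one-sentence repair.

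Nor do the phase 1 rates forecast this trial. They come from a study with several doses and schedules, in which 27.4% of patients died, mostly of progression, and treatment was not limited to two cycles. Here, patients with localized or locally advanced disease receive two cycles. AEs unrelated to treatment may matter much less. Even at face value, a gap of about 0.9 patient is small beside a planned interval 33.8 points wide (46.9 − 13.1), and it does not bear on the sample size.

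A reader might also infer that the primary endpoint cannot be computed. That goes too far. SAEs and dose-altering laboratory events are captured elsewhere, Section 5.3 requires dose changes and missed doses to be recorded, Section 6.1.1 lists AE as a reason for stopping, and Section 9.1.1.1 plans listings or narratives. The AE form even has fields for Grades 1 to 5 and for unrelated events.

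All of this narrows the gap without closing it. Dosing records show that drug stopped; the field described for tying the stop to an AE, action taken, sits on the AE record that Section 8.2.1.3 says not to create for these events. Planned tables and listings cannot supply events that were not recorded.

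**Conclusion.** The point holds as a conflict between AE capture and planned analysis. It should be corrected, but it does not undermine the design. Taken literally, Section 8.2.1.3 leaves the Section 9.1.1.1 tables incomplete and can omit related AEs below Grade 3 that count toward the Section 9 primary endpoint and stopping rule. Any such omission lowers the reported rate; it cannot raise it.

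The effect is 5 points per missed patient if 20 are treated, and one event against the stopping boundary in the cohort concerned. The number missed could be zero. The conclusion assumes that sites follow Section 8.2.1.3 as written and that the discontinuation count draws on captured AEs; the documents do not name another source for it.

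The case for an any-AE estimate rests on the single-arm design and investigator attribution. The 4.3-point phase 1 gap only illustrates its direction.

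**What to change.** 1. Amend Section 8.2.1.3 to record every AE that leads to discontinuation, to non-completion of two cycles or to surgical delay, whatever its grade or attribution. The existing form fields already accommodate this.
2. Reword the Section 8.2 sentence to point to the Section 9 definition, which stays primary, so that both name the same event and the same relatedness requirement.
3. Add to Section 9 the proportion discontinuing for any AE regardless of attribution, with a 90% exact CI, as a stated sensitivity analysis.
4. The table of all treatment-emergent AEs would still omit lower-grade or unrelated AEs that did not affect treatment. Its title should state the capture limit.

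No treatment rule, sample size or stopping boundary changes. The cost is wording in three sections and a table title, AE entries for a few patients, and one extra estimate. The change should be made while these events can still be recorded as they occur.
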